4.1 Hypothesis

Among 282 patients with uncontrolled type 2 diabetes (HbA1c levels > 7%), those randomized to MJS DIABETES, compared to UC, will:

Hypothesis 1 (Primary Aim): Exhibit a higher mean reduction in HbA1c at 12-months.

Hypothesis 2a (Secondary Aim 1): Report higher rates of adherence to self-care behaviors at 12 months.

Hypothesis 2b (Secondary Aim 2): Report greater improvement in diabetes knowledge, self-efficacy and outcome expectation; and more collaborative patient-provider communication, which in turn will be associated with higher rates of adherence and higher mean reduction in HbA1c at 12 months.

4.2 Primary Objective

To compare the efficacy of MJS DIABETES vs. usual care (UC) on HbA1c reduction at 12-months.

4.3 Secondary Objectives (if applicable)

3. To compare the efficacy of MJS DIABETES vs. UC on adherence to self-care behaviors

[figure not shown]
behaviors.

4. To evaluate the potential mediators of the intervention effects (diabetes knowledge, self-efficacy, outcome expectation, and patient-provider communication) on adherence to self-care behaviors and HbA1c reduction.

5 - Study Design

The primary outcome is mean change in HbA1c from baseline to 12 months. Secondary outcomes include 1) changes in patient adherence to self-care behaviors, (e.g., lifestyle behaviors, medication regimen); and 2) theoretical mediators of diabetes knowledge (capability), patient-provider communication (opportunity) and diabetes self-efficacy and outcomes expectations (motivation).

5.1.1 Study Duration (if applicable)

Study Number s18-01044

March 17, 2020 - version 9

The study duration is 24 months. The formative phase will be the first 12 months of the trial to refine the study intervention. The clinical efficacy phase will be 12 months and there will be six patient visits: screening/consent, baseline, 3-month, 6-month, 9-month, and 12-month follow-up.

5.1.2 Number of Study Sites

The study will be conducted at the network of 10 safety-net Family Health Centers (FHC) and Faculty Group Practices (FGPs) at NYU Langone Health.

5.2.1 Primary Outcome Variables

The primary outcome, mean reduction in levels of HbA1c, will be extracted from patients' medical records. We will use the average of 3 glucose readings over the prior 3 months surrounding the study visit date to calculate mean levels of HbA1c.

5.2.2 Secondary and Exploratory Outcome Variables (if applicable)

The secondary outcomes are:

- 1) Patient adherence to diabetes self-care behaviors (e.g., dietary behaviors, medication adherence, foot care), which will be assessed with the self-report measure Summary of Diabetes Self-Care Activities questionnaire
- 2) The theoretical mediators: (a) Patient capability assessed with the self-report diabetes knowledge scale, (b) patient motivation assessed with the self-report diabetes self-efficacy and outcomes expectations scales, and (c) patient perceptions of opportunity (patient-

provider communication) assessed with the self-report Interpersonal Processes of Care survey.

5.3 Study Population

The study will be conducted at the network of 10 safety-net Family Health Centers (FHC) and Faulty Group Practices (FGPs) at NYU Langone Health. English and Spanish are the most common languages spoken with approximately 62% of patients self-identified as Latino, 21% as Black, and 13% as White. Majority of patients have Medicaid. In 2015, the FHCs provided care to 5,218 patients with T2D. Of these patients, 58% had an HbA1c>7% (n=3,026). The FGP consists of at least 657 additional eligible private practitioners in 351 private practices. Approximately, 55% of patients have poor diabetes control.

Selection rationale: The prevalence of T2D has grown to epidemic proportions and is largely considered one of the most significant public health problems in the US, in terms of morbidity, mortality, and economic burden. While a great deal of effort has been spent assisting PCPs in delivering guideline-concordant care to achieve glycemic control, less has been spent facilitating patient's perspective of their disease into care. As a result, an ideal opportunity to improve patient outcomes is being missed in primary care settings, especially among vulnerable populations who suffer disproportionately from its complications. Thus, this study will include diverse English and Spanish-speaking patients who receive care in safety-net practices.

5.3.1 Number of Participants

Study Number s18-01044

March 17, 2020 - version 9

Fourteen PCPs and 36 patients with uncontrolled type 2 diabetes (T2D) from the network of Family Health Centers (FHCs) and Faculty Group Practices (FGPs) at NYU Langone Health will be recruited for participation in the formative phase of the study.

Fourteen PCPs and 282 patients with uncontrolled T2D from the network of FHCs and FGPs at NYU Langone Health will be recruited for participation in the clinical efficacy phase of the study. To mitigate bias, PCPs and patients that participated in the formative phase will be excluded from participating in the clinical efficacy phase.

To meet our patient recruitment goals, we will begin by screening 3,026 patients. We estimate that 40% of screened patients (n=1,210) will satisfy the inclusion criteria, and that 50% of the will have an A1c>7% at baseline visit (n=605). We estimate that approximately 55% of those 363 patients will agree to participate, leaving 282 for our study after accounting for attrition.

5.3.2 Eligibility Criteria/Vulnerable Populations

PCP Eligibility Criteria

Inclusion Criteria: (a) Fulltime primary care provider (MD/DO, NP) practicing at the participating FHCs or FGPs and, (b) Provide care to at least five patients with a diagnosis of T2D.

Exclusion Criteria: Refuse to participate

Patient Eligibility Criteria

Inclusion Criteria:

- Have a diagnosis of T2D for ≥ 6 months;
- Have uncontrolled T2D defined as HbA1c $> 7\%$ documented in the EHR on at least two visits in the past year;
- Fluency in English or Spanish;
- Be willing to send/receive text messages; and
- Be > 18 years of age.

Exclusion Criteria:

- Refuse or are unable to provide informed consent;
- Have acute renal failure, end stage renal disease (ESRD) or evidence of dialysis, renal transplantation, or other ESRD-related services documented in the EHR;
- Have significant psychiatric comorbidity or reports of substance abuse (as documented in the EHR);
- Are pregnant or planning to become pregnant within 12 months;
- Currently participate in another T2D study; or
- Plan to discontinue care at the clinic within the next 12 months.

Study Number s18-01044

March 17, 2020 - version 9

We are targeting social and economically disadvantaged patients due to the high prevalence of T2D and related complications in this population.

We are also targeting employees of the FHCs and FGPs. Primary care physicians (PCP) who agree to take part in this study will not be recruited or consented by any individuals in a supervisory position. Moreover, PCPs will be informed that their decision to participate or to not participate in the study will have no effect on their employment at the FHCs or FGPs.

6 - Methods

6.1.1 Description of Intervention

Formative Phase (Phase 1): Based on the methodology employed in our previous mHealth studies, we will use the evidence-based user-centered design (UCD) approach to systematically gather and incorporate feedback from patients and PCPs for selection and adaption of the appropriate PROs for use in MJS DIABETES. We will use the UCD approach to also optimize and integrate the MJS report into the workflow of the EHR. The formative phase will occur in three sequential steps (Table 2): 1) Focus groups to adapt MJS to diverse patient and PCP needs, including those of Spanish-speaking patients; 2) A design workshop to understand the workflow processes for patients and PCPs and integrate MJS DIABETES into the EHR and patient workflow processes; and 3) Evaluate the usability of MJS DIABETES in a subset of T2D patients and their PCPs to optimize the tool's

performance and workflow integration. The outcome of this phase will be a refined, integrated, and well-tested technology-based PRO system for T2D whose efficacy will be evaluated in the clinical trial efficacy phase.

Table 2. Formative Phase: User centered design (UCD) Tasks and Methods			
Step	Methods	Participants	Outputs
1. Adapt	Focus Groups: 
2 English-speaking patient groups2 Spanish-speaking patient groups2 PCP groups	6-8 patients per group 4-7 PCPs per group	Summary document that specifies: 
Refined PRO contentNeeds, preferences, and barriers/facilitators of use
2. Integrate	Design Workshop 
Workflow mappingProblem/opportunity analysisStory mapping EHR Integration	4 patients 4 PCPs	Design specification document that specifies: 
Clinic workflow/patient journey mapsEssential features of MJS toolMJS prototype
3. Evaluate	Usability testing sessions	4 patients 4 PCPs	
Fully functional MJS DIABETES intervention

Focus groups: We will conduct audiotaped focus groups with patients and PCPs. Four focus groups will be conducted with patients (two with English-speaking patients; two with Spanish-speaking patients; 6-8 patients per group) and two focus groups will be conducted with PCPs (4-7 PCPs per group). Each focus group will be conducted via WebEx, be audiotaped, and last for approximately 2 hours in duration. Patient focus groups will be conducted to identify the barriers and facilitators to uptake of the MJS intervention and inform the initial program content. Patients will be asked to identify the most important symptoms, complications, side effects, and health-related quality of life concerns associated with their T2D and treatment experiences of T2D using validated patient reported outcome

Study Number s18-01044

March 17, 2020 - version 9

measures (e.g., Diabetes Health Profile (DHP)-18) as a guide. In addition, the goal of the focus groups with Latino patients is to culturally adapt the PROs collected in the MJS intervention to needs, experiences and preferences of Spanish-speaking Latino patient users. The PCP focus group will be conducted to elicit feedback on the PROs identified in the patient focus groups, visual representations and placement of the PROs in the EHR, and barriers and facilitators to use in the PCP workflow. All audiotapes from the focus groups and interviews will be transcribed verbatim (and translated into English for the Spanish-speaking groups).

Design Workshop Upon completion of the focus groups, the study team will convene a one-day design workshop in collaboration with Rip Road to further develop the MJS PRO content and ideal workflow integration. The workshop will consist of 4 PCP and 4 patient representatives from the focus groups described above. The workshop will be led by co-I [name] and guided by a UCD protocol that sequentially leads the group through a variety of activities designed to elicit feedback on key components of the MJS adaptation (e.g. paper mock ups of tool design) as well as the proposed clinic workflow/patient journey (e.g., patient "day in the life" map) integration of MJS. Following the design workshop, Rip Road will partner with the study team to embed the MJS-EHR visualizations into Epic.

Usability Sessions: Once the prototypes are created, we will evaluate the workflow processes of the bilingual MJS diabetes intervention via usability testing with a purposive sample of patients and PCPs drawn from the focus group participants. Four patients and four PCPs will complete individual usability sessions with a beta version of the intervention

to provide preliminary performance data on its functioning. Table 4 describes the metrics that will be collected during the testing sessions. Patients and PCPs will also suggest refinements to the mock content and workflow/user journey map from the PCP and patient perspectives — providing key feedback on topics such as potential disruption to the clinic workflow, impact of using interpreter services on discussions of the PRO report, and placement/presentation of the report in the EHR. Our previous studies suggest that we will need four patient and four PCP cycles of usability sessions to reach saturation. Each usability session will be approximately one hour in duration. The primary output of this step is the fully functional, integrated MJS DIABETES intervention for testing in the clinical efficacy trial.

Table 4. Usability metrics	
1.	Task success (effectiveness): % of given task that users successfully complete without critical errors
2.	Time-on task (efficiency): Time taken to complete a given task, measured from the time the user clicks/ texts "begin task" to when she clicks/texts "end task"
3.	Computer/ Mobile phone inputs (efficiency): Raw count of inputs (texts, Mouse clicks, keyboard strokes) and length of the navigation path to complete task
4.	Task completion survey: Post-task ratings of difficulty in a usability test
5.	System Usability Scale: 10-item survey that provides a comprehensive assessment of subjective usability with satisfaction score
6.	Perceived ease of use: 4-item survey that assesses the degree of effort that users perceive is needed to use the tool
7.	Perceived Usefulness: 4-item survey that assesses the perceived benefits and drawbacks of the tool on performing tasks/ job functions
8.	Relevance: 2-item survey that assesses the relevance of the tool on performing tasks/ job functions
9.	Report Quality: 3-item survey that assesses the users evaluation of the quality of the report provided by the tool
10.	Result Demonstrability: 2-item survey that assesses the users perceived ability to explain or talk about the tool with others
11.	Communication: 2-item survey assesses the whether the users communication with healthcare provider improved after using tool
12.	Behavior Intention of use: 4-item survey that assesses the likelihood of using the tool within a specific time frame

Description of MJS DIABETES intervention (Phase 2)

Study Number s18-01044

March 17, 2020 - version 9

Phase 2 of the study will not begin until all materials for this phase have been fully developed. These materials will then be submitted to the IRB via a modification for review and approval.

Patient intervention: MJS DIABETES is comprised of 5 components: 1) PRO assessments, sent via text message; 2) adherence text message assessments; 3) data-driven feedback text messages 4) motivational text messages; and 5) journal reports that visually display PRO data.

MJS helps patients (and their provider) see how their diabetes symptoms and psychosocial functioning are changing overtime. Participants who enroll in the study agree to have messages sent to their phone based on one of several PRO categories. These include: (1) diabetes quality of life; (2) overall emotional health; (3) lifestyle behaviors; (4) medication adherence; and (5) physical functioning. PRO questions will be sent on a daily or weekly basis, depending on the PRO (i.e., adherence is a daily measure while quality of life is sent on a weekly basis). The list of potential PROs that will be sent to patients over the course of the 12-month study and their primary questionnaire source are shown in the Table below. No PHI will be collected in the MJS DIABETES tool. All data is a numerical response that is anonymous.

Potential MJS PROs	Scaling	Source
Over the past week, how would you rate your level of fatigue because of your diabetes?	0 (not at all tired)-10 (extremely tired) scale	Global Health PROMIS Tool
How would you rate your sleep quality over the past 7 days?	0 (very poor)-10	NIH PROMIS Sleep

	(excellent) scale	Quality
Over the past week, how often were you able to take your diabetes medication on time?	Never Rarely Sometimes Often Always	Diabetes self-management questionnaire
How many of the last seven days have you followed a healthful eating plan for diabetics?	0-7 days	Summary of Diabetes Self-Care Activities
In general, my present quality of life is	As good as it can be Good Quite good Neither good or bad Quite bad Bad As bad as it could possibly be	Audit of Diabetes Dependent Quality of Life
Over the past week, how often were you been bothered by emotional problems such as feeling anxious, depressed or irritable because of your diabetes?	Never Rarely Sometimes Often Always	Global Health PROMIS Tool
Over the past week, what percent of the time did you take all your diabetes medications as your doctor prescribed?	0-100%	Self-Rating Scale Item
On how many of the last seven days did you take the correct number of (pills/injections) for this medication?	0-7 days	Summary of Diabetes Self-Care Activities
Over the past week, how often did you eat [favorite unhealthy food]?	Always Often Sometimes Rarely Never	Perceived Dietary Adherence Questionnaire

Study Number s18-01044

March 17, 2020 - version 9

On how many of the past 7 days did you eat lots of sweets or other foods rich in carbohydrates?	0-7 days	Perceived Dietary Adherence Questionnaire
How effective are you in coping with your diabetes?	1 (not at all) to 5 (extremely effective)	Appraisal of Diabetes Scale
How many times over the past week did you eat desserts like cookies, cakes and muffins or other sweets? Do not include sugar free kinds.	Never 1 time 2-3 times 4 or more times	NHANES Dietary Screener Questionnaire
How many times over the past week did you refined carbohydrates like white bread, white flour tortillas, dinner rolls and bagels?	Never 1 time 2-3 times 4 or more times	NHANES Dietary Screener Questionnaire
On how many of the past 7 days did you space carbohydrates evenly throughout the day?	0-7 days	Perceived Dietary Adherence Questionnaire
Over the past week how well could you control your emotions?	Not at all Poorly Fairly well Very well Extremely well	Thrive Questionnaire
In general, how would you rate your mental health, including your mood and your ability to think?	Poor Fair Good Very good Excellent	Global Health PROMIS Tool
How much was the quality of life of your life affected by the time required to control your diabetes?	0 (Not at all affected) – 10 (as bad as I can be)	Patient-reported outcome-Quality of Life
Over the last week, did you experience any weight gain because of your diabetes	Always Often	Diabetes Impact Measurement Scales

	Sometimes Rarely Never	
Over the last week, did you feel irritable or moody because of your diabetes	Always Often Sometimes Rarely Never	Diabetes Impact Measurement Scales

In addition to the PRO questions, patients will receive feedback via motivational and data-driven text messages. These text messages are designed to activate patients in their care via continued participation in the MJS program, and to provide them feedback data on patterns in their responses for self-reflection.

We have developed and tested three types of data-driven feedback messages that were automatically sent to patients on a weekly basis describing patterns in their PRO assessments over the past week. The high/low comparison messages compared the lowest (shortest) value reported (to date) to previous weeks, in which higher (longer) value were reported. The weekly average comparison messages compared changes in patients' mean PRO ratings for the current week as compared to the previous week. The re-occurring values messages also compared multiple weeks over time, data from single days during the week to days in previous weeks, and multiple [single] days over time. We use a rule-based algorithm that searches for these patterns in patient's data on a weekly basis. Specifically, the high/low comparison and re-occurring value messages will be sent if the appropriate patterns in the data are identified for the current week. If no patterns in the data are

Study Number s18-01044

March 17, 2020 - version 9

identified, the weekly average comparison message will be sent as the default message each week. Example messages from our pilot include the following:

Comparison High/Low Message: Last [day of the week] your average FATIGUE score was a "[numerical fatigue score]." That is the lowest score you have reported in the past [#] of weeks.

Comparison Multiple day Message: In the past week your FATIGUE scores have been: "[day of week – numerical fatigue score for that day]"; "[day of week – numerical fatigue score for that day]"; and "[day of week – numerical fatigue score for that day]".

Average PRO value Message: Your average FATIGUE score this week was a "[numerical fatigue score]", compared to your average fatigue score of "[numerical fatigue score]", last week.

Motivational messages are also automatically generated and delivered via a pre-specified algorithm. There are two categories of motivational messages: (1) Response-based (i.e., sent in response to high/low compliance in replying to assessment entries) and (2) % completed (i.e., sent after specified time intervals of participation). Example messages include:

Low Compliance Message (always triggered if 3 consecutive days are missed): We haven't heard from you in the last 3 days. Text HELP if you need assistance in the journaling program.

Good Compliance Message: You have answered 10 text messages in a row for the

Good Compliance Message: You have answered 12 text messages in a row for the journaling program. Keep it up!

% Completed Message 1: You have responded to 85% of the messages over the past 4 weeks in the journaling program.

% Completed Message 2: Congratulations! You are halfway through the journaling program.

Mobile Opt-in/Opt out Process: After completing informed consent, patients randomized the intervention condition will meet with the RA to receive training on how to use the intervention and opt in to receive SMS messages. Per carrier policies to opt in, patients must provide their mobile numbers and carrier information. Once their information has been added to the system, they will receive a SMS asking them to reply to confirm their participation. To confirm, patients will need to reply via text message.

This step verifies their mobile number and joins them to the intervention. They will receive a welcome message.

To cancel or opt out of the program at any time, patients will be required to send the word 'STOP' to any program message. This information is communicated to the patient at the time of registration, via a Mobile Terms and Conditions document – which they will be required to sign. The opt out information is also communicated to them within the first program confirmation SMS, as well as once a month, in a SMS message sent as part of their subscription service.

Study Number s18-01044

March 17, 2020 - version 9

All additional carrier compliance terms will also be adhered to. A HELP message, and an invalid response message will be developed. Carrier specific rate information will be included in messages as required.

Patients will then be instructed on how to respond to the SMS messages and asked to demonstrate their ability to understand.

Journal report: After the first week, and every 2 weeks thereafter, patients will receive a journal report that visualizes their responses to the text message questions in straightforward graphs and displays the adherence responses in a calendar. The reports are intended to help patients reflect on changes in their responses overtime, and discuss how their symptoms and functioning have changed in between visit.

PCPs: The EHR-integrated journal reports will provide PCPs with quantitative assessments of the extent to which patients are adhering to their T2D regimen, the psychosocial factors that may inhibit adequate glycemic control, and the diseases impact on their functional status. Reports of patient PRO data will be uploaded to the EHR every two weeks. Providers will be able to access reports of patients' PRO data via the MJS-EHR interface during visits with the patient or asynchronously to track patients' PROs between visits. Based on our pilot data, we will encourage providers to use the reports to support patient engagement and shared decision-making in the clinic visit, set priorities for the visit, and discuss trends in PRO data as they relate to behavioral and clinical outcomes. Prior to the initiation of the trial,

all participating PCPs will receive standardized training in the MJS-EHR interface functionalities as well as best practices for patient-centered discussions of the data visualizations (Table 6). The ability to receive and review PRO reports between clinic visits may also offer several opportunities to improve patient care such as by: reducing critical information gaps about patients' condition or symptoms; supplementing existing clinical data; providing PCPs with a comprehensive view of patients' ongoing experience of their

Study Number s18-01044

March 17, 2020 - version 9

illness (symptoms, function and well-being); as well as meeting meaningful use requirements for two-way electronic communications.

Description of UC group

Patients randomized to the UC group will receive standard diabetes treatment recommendations as determined by their PCP. Rationale for UC condition: The UC group was designed to mimic usual care as delivered in primary care practices. We believe that including an alternate approach such as an attention control condition would defeat the purpose of this trial, which is to compare the efficacy of an innovative approach to collect and track PROs for diabetes self-care in real-world practice-based settings with particular attention to its integration into standard clinical practice.

Table 6. Treatment Fidelity Strategies

Element	Strategy
Study design	Conduct usability testing in Phase 1 of MJS Ensure MJS is consistent with TAM and SCT theoretical constructs Develop protocol for identifying and resolving technical problems during the study Distribute password protect study cell phones to ensure UC group patients are not given access to the MJS program during the study Limit access to the MJS EHR interface via a password protected portal Develop system prompts that direct PCPs to the appropriate interface (MJS vs. UC) for the patient being seen Embed quality control checks into the EHR to track whether UC patients receive the intervention despite the system prompts.
Participant training	Patient: 1:1 in-person training in the use of MJS using a standardized manual. Handout outlining program expectations, instructions on how to read the journal report, a toll free study phone number, and a link to an internet-based video that reviews the training content PCP: Internet-based, standardized training videos that will be archived and available for booster trainings. Training topics will include: demonstrating how to view and print MJS journal reports for use with participating patients during clinic visits, explaining how to interpret the reports, and best practices for patient-centered discussions about the data visualizations in the report.

	discussions about the data visualizations in the report
Intervention delivery	Continuous monitoring of MJS EHR interference and texting program to ensure program is working correctly and being delivered consistently Immediate resolution of technical difficulties
Intervention receipt	Collection of patient (i.e., # of texts delivered, error messages received, time to complete PRO messages) and PCP (i.e., # of MJS EHR interface log ins) usage metrics
Enactment of intervention skills	Audiotape a random sample of 20% of clinic visits to assess use of the journal report Collection of patient (i.e., # of texts sent in response to PROs messages, TAM3 survey about use behavior) and PCP (i.e., EHR data observing their time interacting with the MJS interface) engagement metrics

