6.1.2 Method of Assignment/Randomization

This project has a hierarchical study design with each patient nested within a PCP thus, randomization will occur within PCP. The study statistician ([name]) will oversee randomization, which will be carried out using a SAS macro after completion of the consent procedures and baseline data collection. Patients will be randomly allocated to either the intervention (MJS DIABETES) or UC at a 1:1 ratio. A random number from 0 to 1 will be used to determine to which group the subject is assigned. The standard cut score will be set at 0.5 for the first n subjects from the same PCP. Those who receive a random number between 0 and 0.5 will be assigned to the UC group and those with a random number greater than 0.5 will be assigned to the MJS group. The balance between the groups within each PCP will be carefully weighted after the total number of subjects from a PCP reaches a number greater than n. Before the randomization procedure, the number of subjects randomized to each arm of the study for each PCP will be estimated using SAS macro programs. If more than the n subjects are randomized initially, the cut score for the next subject is equal to the ratio of the experimental arm (n1) to the subjects already randomized

(m) for that PCP (n1/m). The randomization log will be stored in a secure file, and will be password protected. Once a patient has met eligibility criteria and provided consent, the program manager will call the study statistician for the patient's group assignment. As is true for most behavioral interventions, the patient cannot be blinded to the group assignment. However, it is plausible that study staff could bias the study outcome by knowing the patient's group assignment. To mitigate the potential for this bias, the RA that is responsible for data collection will be blinded to the patients' group assignments and study hypotheses (i.e., single blind design).

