To increase enrollment into the study, all participants will also be asked about their ability to receive text messages during the consent procedures. Those individuals who express concern about participating due to the fees associated with receiving text messages (due to either not having a text messaging plan or a limited allowance of messages per month) will receive reimbursement for the messages that are sent as part of the study. Patients who will accrue the most text messaging charges and do not have a text messaging plan will be reimbursed \$25 in total.

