For the clinical efficacy phase, the primary analysis is intent-to-treat (ITT). For the ITT approach, all patients that are randomly assigned to the intervention or UC groups will be included in the analysis, regardless of program and evaluation compliance. The primary outcome is the mean reduction, compared to baseline, in HbA1c at 12 months in the MJS diabetes intervention vs. UC arm. HbA1c will be treated as a continuous variable in this analysis. We will test the treatment X time interaction in a random effects linear regression model to test the time-specific differences in HbA1c at 12 months attributable to the intervention. We also will use the "lincom" command in Stata to estimate differences in time-specific changes from baseline. In additional analyses, we will adjust for covariates (e.g., ethnicity, gender, age, income, education, employment, insurance) unbalanced between the treatment arms at baseline at $p=0.10$.

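### The first working check that a patient can text comes after randomisation and only in the MJS arm; one test exchange for everyone beforehand would reduce dilution cheaply

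*Combined protocol and SAP*

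**What the plan says.** **Before randomisation, both arms.** Section 5.3.2 makes texting an entry criterion: "Be willing to send/receive text messages". Section 6.3.4 adds that "all participants will also be asked about their ability to receive text messages during the consent procedures". That question is there to help enrolment. It leads to reimbursement of messaging charges, and no exclusion is attached to it.

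**Randomisation.** Under section 6.1.2 it is "carried out using a SAS macro after completion of the consent procedures and baseline data collection". Section 6.3.5 gives the same order: consent, baseline measures, allocation. Neither section lists a text exchange before allocation.

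**After randomisation, MJS arm only.** In the opt-in part of section 6.1.1, "patients randomized the intervention condition will meet with the RA to receive training on how to use the intervention and opt in". They supply a number and carrier, sign the mobile terms and receive a text. "To confirm, patients will need to reply via text message". The protocol then says: "This step verifies their mobile number and joins them to the intervention".

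**Analysis.** Under section 6.4.3.1, "all patients that are randomly assigned to the intervention or UC groups will be included in the analysis, regardless of program and evaluation compliance". No rule covers an MJS patient who does not confirm, and section 6.4.2 allows for attrition but not for non-starters.

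**The concern.** Willingness to text is a condition of entry, but whether it works in practice is tested only once the patient is in the trial, and only in one arm. Four of the five MJS components in section 6.1.1 are text messages. The fifth, the journal report, displays what patients text back, and the report that the PCP sees in the EHR uses the same data. A patient who is not joined to the programme therefore receives essentially none of the intervention but contributes to the MJS mean.

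What is at stake is the size of the MJS-UC difference and the power to detect it. The trial already intends a texting population, so patients who prove unable to text after allocation add noise that a short check could have prevented. Some such patients are plausible: section 5.3.2 targets socially and economically disadvantaged patients, and section 6.3.4 expects some to have no texting plan.

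**Working it through.** **Inputs from section 6.4.2:** group difference 0.6%, SD 1.6%, 5% type I error, 80% power, 113 per group, 20% attrition, 282 patients (141 per group). Sidedness is not stated.

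**Step 1: reproduce the plan's figure.** Two-sided normal approximation: n = 2 × (1.96 + 0.8416)² × 1.6² / 0.6² = 111.6, so 112 per group. The exact two-sample t test gives 112.6, so 113, with power 80.1% at 113. A one-sided test gives 88, so the plan used a two-sided test. For attrition, 113 / 0.8 = 141.25 per group, in line with the stated 141.

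**Step 2: dilution.** Let f be the share of the MJS arm that never confirms. If those patients get no effect and are followed up, the expected difference is 0.6 × (1 − f). The documents give no value for f; the rates below are assumptions.

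**Step 3: power at 113 per group.** The standard error is 1.6 × √(2/113) = 0.2129. For f = 5%, 0.57 / 0.2129 = 2.68, and Φ(2.68 − 1.96) is about 76%. The t-test results are:

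| Assumed f | Patients of 141 | Expected difference | Power | Completers per group for 80% |
|---|---|---|---|---|
| 0% | 0 | 0.600 | 80.1% | 113 |
| 2% | about 3 | 0.588 | 78.5% | 118 |
| 5% | about 7 | 0.570 | 76.0% | 125 |
| 10% | about 14 | 0.540 | 71.4% | 139 |

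**Step 4: a point of reading.** Section 6.4.2 words 282 as the number who complete, but 282 × 0.8 = 225.6, or about 113 per group, so the arithmetic makes 282 the number enrolled. If 141 per group really did complete, power would be 88.1% with no non-starters and 80.6% at f = 10%.

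**The case against.** The strongest reply is that non-starters should be rare. Everyone has stated willingness to send and receive texts, ability to receive them is asked about at consent, and charges can be reimbursed. Sign-up takes place with a research assistant. Table 6 adds one-to-one training, a toll-free number, prompt technical help and study cell phones. A willing patient who fails to answer one text in that setting would be unusual. This stands, and it is why the loss is probably at the low end of the table. It does not close the gap: the pre-randomisation safeguards are self-report, the question at consent covers receiving and not replying, the phones are listed to prevent contamination, and the help comes after allocation.

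A second reply is that the power figures may overstate the loss. Section 6.4.2 gives 0.6% to 1.4% as a difference between groups, not as an effect in patients who start. If that figure already reflects some non-uptake, multiplying by (1 − f) counts it twice. The 0.6% is also the bottom of the expected range: at 1.0%, even 20% non-starters leave a difference of 0.8% and power of about 96%. Non-starters who also drop out would overlap with the 20% attrition. All of this stands.

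A third reply is that intent-to-treat is deliberate. The rationale for usual care in section 6.1.1 stresses real-world practice, where failed sign-up is part of the effect. This also stands: narrowing entry to confirmed texters is a trade-off.

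A reader might infer three stronger things that the documents do not support:
- That the primary comparison is biased. It remains valid for the effect of assignment.
- That the opt-in step causes one-sided withdrawal from the trial. STOP cancels the programme, and section 6.1.3 takes HbA1c from the EHR, with a lab test if a follow-up value is missing.
- That a test text would abolish the dilution. It cannot, because the opt-in itself stays after allocation.

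**Conclusion.** The point holds as a verification gap and a cheap improvement, not as an error in the analysis. The first working check of texting follows randomisation, applies to one arm, and has no rule for patients who do not pass it. The cost is dilution of unknown and probably small size: about 1.6, 4 or 9 percentage points of power at assumed non-start rates of 2%, 5% or 10%. These figures rest on four assumptions: the rates themselves, no effect in non-starters, complete follow-up of non-starters, and a planned 0.6% difference that does not already include non-uptake.

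**What to change.** In section 6.3.5, with a matching line in 6.1.1, require every patient to send and receive one test text with the study number during the consent/baseline visit, before the call to the statistician for allocation. Describe it as the check of the existing texting criterion in section 5.3.2. It needs no particular visit format: section 6.3.2 describes consent both by telephone and in person, and the exchange works either way. Keep the MJS opt-in and the mobile terms for the MJS arm after allocation, so that UC patients are neither joined to the programme nor asked to sign terms for it.

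The change needs protocol wording and one exchange per patient, with no new staff or added patients. The downside is a few minutes for UC patients and a result that applies to patients confirmed able to text, which matters in a safety-net population. Some patients may still not complete the opt-in, and later STOP messages or non-response are untouched.
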